## Subject’s Capacity to Give Legally Effective Consent

To be eligible, subjects must be able to give legal effective consent.

## Risk/Benefit Assessment

Risks in this study may arise from 1) the assessment interviews and questionnaires, and 2) discussing and hearing recent personally distressing events.

The assessment interviews and questionnaires may be stressful for some people. Some individuals may experience increased emotional discomfort as they discuss past or present problems during the assessments. During each in-person assessment, a trained professional will be available for consultation should discomfort become extreme.

## Minimizing Risks

All participants will be asked to read, discuss, and sign written consent forms that describe the study procedures. Assessors will first give a narrative of the consent, and then have the subjects read it themselves. Following this, assessors will summarize the consent and answer any questions the subjects may have. The written document will not be signed until all questions and study concerns have been addressed. All participants will be told that they are free to withdraw from the study without penalty at

any time. Every effort will be made to make the environment comfortable and supportive during assessment procedures: snacks and beverages may be offered, breaks will be taken, and the assessment will be stopped if the subject wishes or if stress is too high. All assessment sessions will be video recorded and will be supervised via regular weekly study meetings with [name] and other study staff. However, subjects will be afforded the option during the informed written consent process to opt out of being audio or video recorded and still remain in the study.

As a necessary aspect of participation in this study about emotion regulation, participants will be asked to describe and subsequently hear personally upsetting stories. This aspect of the study will be clearly delineated in the consent form and the study staff member obtaining consent will verbally describe this aspect of the study to each prospective participant. Participants are also free to discontinue the study at any time. Should a participant's discomfort become extreme and includes strong thoughts of suicide, a trained professional will be available on-site during all active study hours. Because suicidal ideation is an exclusion criterion, we do not expect this to be likely risk. We will be using the Suicide Risk/Distress Protocol along with the SCID-I to assess suicidal ideation, intent, self-harm, and date of most recent attempt at the beginning of the assessment day and at the end. In the rare event that a high rating of ideation or distress occurs, the trained study staff will work with [name] and the participant to address these suicidal thoughts and if they are deemed to be at imminent risk of suicide after the conversation, we will call 911 or obtain a commitment from the participant to go to the nearest hospital emergency room, (e.g. Duke ER). We will also use the Suicide Risk/Distress Protocol to assess ideation, intent and self-harm at pre and post the intake and laboratory sessions.

Study-related adverse and serious events are not expected but will be closely monitored and will be reported to the proper authorities according to established FDA guidelines. All information gathered in this study will be maintained in the research record.

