Subjects who endorse suicidal ideation but deny intent and plan will be included in the study. Subjects who are at high risk for self-harm, endorsing intent and plan, will be excluded from the study. Subjects who report a suicide attempt within the past 6 months, will also be excluded. For the subjects who are at current high risk for self-harm (i.e., intent to kill oneself is rated higher than a 4 on a 7-point scale while the assessor is going through the Suicide Risk and Distress Protocol or subject states that s/he is uncertain about being able to control suicidal impulses), assessors will complete the Suicide Assessment Worksheet and follow the instructions outlined in the Suicide Risk and Distress Protocol. This is also discussed under the minimizing risks section of this document.

Protocol violations that could represent serious or continuing noncompliance will be brought to the attention of the PI as soon as possible and not longer than 24 hrs. These violations will be reported to the Duke University Medical Center Institutional Review Board using the appropriate documentation within 5 days of notification of the PIs.

Reporting of non-study related, non-serious AEs are not reported to the IRB, and not entered on the study AE tracking log.

Non-serious AEs that are deemed study related will be reported to the PI with annual reporting and entered into the study AE tracking log. These will be reported to the IRB as needed.

Protocol deviations around study visit windows, skipped questions on self-report measures, missed therapy sessions, etc. will not be reported to the Duke IRB. Other protocol deviations will be reported to the PIs upon discovery and will then be reported to the Duke IRB within 2 weeks.

In this study, if a subject experiences an SAE or study related, non-serious AE and they are not resolved at their final study visit, because it is a minimal risk study, we do not plan to continue to follow the event past their final study visit.

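### The low-risk rationale says suicidal ideation is excluded, yet some people with ideation are eligible, and the stated exclusion does not match the plan's own description of high risk

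*Combined protocol and SAP*

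**What the plan says.** Three places in the combined protocol and SAP bear on this.

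- **Selection of Subjects**, exclusion 4, names current suicidal ideation but refers the reader to the data and safety section for the specific criteria. Exclusion 5 removes anyone with a psychiatric admission in the previous 6 months.
- **Minimizing Risks** considers the possibility that a participant's "discomfort become extreme and includes strong thoughts of suicide" and comments: "Because suicidal ideation is an exclusion criterion, we do not expect this to be likely risk". It also describes a trained professional on the premises, suicide-risk assessment before and after sessions, and emergency escalation.
- **Data & Safety Monitoring**, under Suicide Ideation & Risk, gives the criteria themselves. On inclusion: "Subjects who endorse suicidal ideation but deny intent and plan will be included in the study". On exclusion: "Subjects who are at high risk for self-harm, endorsing intent and plan, will be excluded from the study". An attempt in the preceding 6 months also excludes. A further sentence opens "For the subjects who are at current high risk for self-harm" and explains that status as either "intent to kill oneself is rated higher than a 4 on a 7-point scale" or "subject states that s/he is uncertain about being able to control suicidal impulses". The action stated for this group is that "assessors will complete the Suicide Assessment Worksheet and follow the instructions outlined in the Suicide Risk and Distress Protocol".

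**The concern.** There are two problems. First, the only reason offered for the low-risk expectation is that ideation is excluded, and the criteria do not exclude it as such. Second, high risk is described in two ways a couple of sentences apart. Exclusion is attached to the narrower description, and only management steps to the broader one.

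This matters because of what participants are asked to do. They listen repeatedly to recordings of their own recent stressful experiences: three presentations of each under the general description of the stressor task, and between 2 and 4 in the Habituation condition. They are selected for marked emotion dysregulation (DERS total of 90 or more), and 22.1% of the predecessor study's sample had current major depression. That is not an ideation rate, but it makes it plausible that some participants will have ideation.

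The IRB should be given a risk rationale that is true of the people enrolled. An assessor should be able to reach one eligibility answer for someone the protocol calls high risk.

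**Working it through.** No arithmetic applies. The check is a comparison of the sections.

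**Step 1: which text governs eligibility.** Selection of Subjects lists ideation as exclusion 4 but hands the specifics to Data & Safety Monitoring. The latter is therefore the operative rule. The cross-reference also means that these two sections need not be read as contradicting each other.

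**Step 2: test the rationale against that rule.** The rationale in Minimizing Risks requires that people with ideation are not enrolled. The operative rule says "Subjects who endorse suicidal ideation but deny intent and plan will be included in the study". For anyone with ideation who denies both, the premise is false. The cross-reference does not rescue it, because the sentence relies on ideation itself being excluded, not on the narrower set of exclusions that apply.

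**Step 3: compare the two descriptions of high risk.**

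| | First description | Second description |
|---|---|---|
| Content | Intent and plan endorsed | Intent above 4 of 7, or uncertain impulse control |
| Is a plan needed? | Yes | No |
| Is intent needed? | Yes | Not on the second limb |
| Stated consequence | Exclusion | Worksheet and risk-protocol steps |

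**Step 4: apply both to particular people with current ideation and no recent attempt.**

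- *Intent and plan denied, impulse control not in doubt.* Included. The sentences agree.
- *Intent and plan both endorsed.* Excluded by the first description.
- *Intent and plan denied, uncertain of controlling suicidal impulses.* The inclusion sentence admits this person. The second description calls the same person high risk. The two limbs of that description are joined by an or, so intent is not needed to meet it.
- *Intent rated above 4, no plan.* High risk on the second description, but short of the stated exclusion, which requires a plan as well. The inclusion sentence does not cover this person either, because intent is not denied.

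The third person has two conflicting answers. The fourth has no express one.

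**The case against.** The best defence of the rationale is that it is shorthand: it cites exclusion 4 by name and leaves the content to the data and safety section. The event called unlikely is also narrower than ideation, and the sentences that follow plainly provide for ideation being found. This has some force. The conclusion may well hold, given the exclusion of intent with plan, of a recent attempt and of a recent psychiatric admission. But Minimizing Risks does not cite those exclusions. It cites one that the criteria do not apply as stated.

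The best defence of the criteria is that the second description only triggers safety management, or alternatively that it defines high risk and so brings such people within the exclusion. Each reading is possible, but they give opposite answers on eligibility, and the text does not choose. The Suicide Risk and Distress Protocol, a separate document not available for this review, may settle how assessors handle these people. That is a real limit on the point. However, Selection of Subjects places eligibility in the data and safety section, so the rule should be clear there.

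It is also fair to say that excluding uncertain impulse control is a clinical choice. The proposal below follows the protocol's own label of high risk and imposes no outside standard.

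Three stronger readings are tempting, and the documents do not support them:

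- *That participants are unprotected, or that the risk is in fact likely.* The safeguards are described, and training also opens with a question on suicidal urges. Only the stated reason is wrong.
- *That everyone with intent alone or plan alone is clearly admitted, or clearly excluded by default under exclusion 4.* The text states neither. Intent is also a 7-point rating, so a yes/no tally of cases would misrepresent it.
- *That the number affected can be estimated.* No ideation rate is given. Any count from an assumed rate would mostly cover people the protocol deliberately admits, and would not measure the inconsistency.

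**Conclusion.** The point holds as a safety and eligibility inconsistency that should be corrected. The sole reason given for the low-risk expectation is untrue of eligible people with ideation who deny intent and plan. The express exclusion is also narrower than the protocol's own description of current high risk. Read literally, the text can enrol someone it calls high risk into a repeated personal-stressor task.

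Its size cannot be expressed as a number of participants. It concerns one rationale sentence and two identifiable kinds of person. The conclusion assumes that the data and safety section is the operative eligibility rule, as the cross-reference in Selection of Subjects indicates, and that the separate risk protocol does not itself set eligibility.

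**What to change.** **Data & Safety Monitoring.** Replace the two descriptions with one rule. A person is excluded if they endorse intent or a plan, have an intent rating above 4 of 7, are uncertain of controlling suicidal impulses, or have made an attempt within 6 months. Ideation is compatible with enrolment only when intent and plan are both denied and none of these markers is present. Keep the worksheet and risk-protocol steps as the response for anyone who meets a high-risk marker.

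**Minimizing Risks.** Say openly that people with ideation but no intent, plan or high-risk marker are enrolled. Rest the low-risk expectation on the exclusions that apply (the high-risk markers, a recent attempt, a recent psychiatric admission) and on the safeguards already described.

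**Cost.** An IRB wording amendment to two sections, and a few high-risk people who become ineligible. The safeguards, sample size and analysis do not change.

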#### Potential Benefits

Participants will be contributing to our understanding of the way that mindful breathing may improve the ability to perceive other people's emotions. As part of the study design, the participants randomized to receive the mindful breathing intervention and the perspective-taking induction (the active comparison group) will learn useful skills to help regulate their emotions or improve their relationships, as hypothesized. Participants randomized to the control condition (the worry induction) may benefit from monitoring their emotional state repeatedly throughout the study, which may increase emotional awareness.

#### Costs to the Subject

Participants will incur no costs for participating in any phase of this study.

## Data Analysis & Statistical Considerations

For the primary outcome of biases in emotion perception, the estimates were derived from a mean difference between conditions. With a Type-I error rate of 5% and 72 participants (24 per group), we will have at least 80% power to detect a medium to large effect size (Cohen's  $f = 0.38$ ), based on previous research demonstrating negative biases in emotion perception using similar behavioral measures. (Schmid & Schmid Mast, 2010) Because we anticipate a 10% to 15% rate of dropout, 30 participants will be randomized to each group. Therefore, this study will recruit 90 adult participants over the age of 18 who have high emotion dysregulation and interpersonal problems.

Since 2004, the CBTRP has recruited a range of adult psychiatric samples all characterized by problems with emotion regulation. Across studies of emotional functioning, it is estimated that our lab has run over 980 participants since 2004, at a rate of roughly 90 per year. In our previous NIMH project, over 33 months we have screened 1154 individuals and enrolled 169 participants, at a rate of 5.12 per month. We project enrolling 90 participants over 14 months, at a rate of 6.43 per month. Given our demonstrated track record of success meeting the required recruitment target in the present application, we expect to meet recruitment targets in the proposed project.

Specific Aim 1: Aim 1 will determine if the emotion regulation intervention leads to fewer negative biases in emotion perception during the laboratory training session. For this aim, we will conduct ANCOVA analyses to study group differences in performance on the emotion perception laboratory tasks, controlling for their baseline scores assessed in the intake session. To compare the conditions' impacts on negative biases, we will analyze group differences in 1) number of trials with neutral facial expressions are misclassified as negative emotions; 2) accuracy for positive emotions and negative emotional expressions. We will also examine the relationship between emotional distress and emotion perception. Hypothesis 1: Participants in our emotion regulation condition will have less negative bias in emotion perception (e.g. fewer neutral faces misclassified as negative, lower accuracy for negative emotions, higher accuracy for positive emotions) compared to participants in both the control conditions. Even though the perspective-taking and mindful breathing conditions may have similar effects (e.g. increasing attention to social cues (Olsson et al., 2016; Quaglia, Goodman, & Brown, 2016)), perspective-taking inductions may still lead to mood-congruent biases by increasing negative emotional responses (Lamm, Batson, & Decety, 2007). Therefore, we predict that the emotion regulation intervention would reduce this bias significantly more than both the worry and perspective-taking conditions. We also predict that intensity of emotional distress will be related to negative biases in emotion perception.

Specific Aim 2: Aim 2 will compare the changes in emotion perception over time between the emotion regulation breathing condition and the control conditions. For this aim, Multilevel modeling (MLM) will be used because it permits evaluation of longitudinal data on participants over time with trajectories for each participant examined as random effects. We will conduct MLM analyses to study group differences in changes in the laboratory emotion perception tasks assessed during intake (time 1), the training session (time 2) and after the testing phase (time 3). For the phone-based behavioral task, we will first examine the psychometric properties of this measure in this clinical sample. Then, we will analyze group

differences in the valence of emotion perception ratings over the one-week testing phase. We will also examine whether changes in emotion dysregulation and distress mediate changes in negative biases over time. Finally, we will also explore the effects of the intervention on self-reported psychological and social functioning. Hypothesis 2: One week of hearing the tones via mobile phones will lead to greater long-term changes in negative biases emotion perception for participants in the emotion regulation condition compared to the participants in the control conditions. Changes in emotional regulation and distress over time will mediate changes in negative biases in emotion perception over time.

If our hypotheses are not supported and the conditions do not have significantly different effects on emotion perception, these findings would be indicative of trait-like deficits in emotion perception beyond the momentary effects of mood or perspective-taking. We would then use moderation analyses to explore the role of other stable factors within emotion perception performance, such as trait empathy (measured by the IRI) or psychiatric diagnoses.

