## Design & Procedures

This study is funded by Duke University Bass Connections Project Teams, through Duke Institute for Brain Sciences (DIBS). It is also funded by the Varela Award from the Mind & Life Institute.

**Study Overview:** This study will be a three-group study and will broadly follow the protocols of our team's previous study, "Evaluating a Novel Method of Generalizing Emotion Regulation" (Pro000035922). The study will be conducted over two sessions in the lab (intake and training sessions), followed by one week of receiving mobile phone prompts (testing phase). In the first intake session, all participants will be assessed for psychiatric diagnoses and complete the emotion perception tasks. Then, the participants will return one week later for the training session. Participants will be randomized to one of three groups: 1. Mindful Breathing, 2. Habituation, or 3. Control condition. After the training session, all participants will receive mobile phone prompts during the one-week testing phase. At the end of testing phase, all participants will complete the self-report measures of psychological functioning and the emotion perception tasks through an online survey. Emotional distress will be measured repeatedly throughout the study. See figure for a summary of the main procedures in the study protocol, with measures that may be used in primary and exploratory analyses:

**Recruitment and Assessment.** Before being recruited into the study, potential participants will complete a phone screen—a pre-experiment screening questionnaire (see Phone Screen document) or complete an online survey done through Qualtrics to assess certain exclusion and inclusion criteria (see inclusion/exclusion criteria in section 5). As the phone screen collects PHI (e.g. name, email and/or telephone number, knowledge of psychological symptoms, etc) in order to determine eligibility for the study, we request the waiver of consent to collect this information prior to informed consent. Potentially eligible participants will come to the lab for their intake session to fully determine eligibility for the study (see Request for Waiver of Consent). Upon arrival, a Clinical Assessor ([name] or [name]) will review the consent form, answer any questions, and obtain written informed consent. The Clinical Assessor then will administer diagnostic interviews (i.e. Structured Clinical Interview for

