#### Experimental Procedures

Intake Session: After determining eligibility, participants will complete measures of social and psychological functioning (DERS, IRI, PANAS-2, TMS, AIHQ-A, NIH SRS, PHQ-9, BES, EMT, SIAS, PFQ) and the two laboratory emotion perception tasks (BLERT, EPBT) through an online Qualtrics survey on a standard desktop computer in the laboratory. At this time, they will provide four recent stressful experiences for the personalized stressor task.

Training Session: All participants will come back to their lab for this session (ideally between 5-7 days after the intake session), which will take approximately 1.5 hours. First, all participants will be asked about: 1) current distress and suicidal urges (i.e. Suicide Risk Protocol), 2) any changes in medications since the previous visit, 3) nicotine, caffeine, and alcohol use that day, 4) subjective units of general psychological distress (SUDS; visual analogue scale from 1-9), 5) dissociation state, assessed using self-report (Dissociative-Tension States Scale 4 item version-DSS-4 from the DSS-acute), 6) levels of arousal with the Sedation Scale, and 7) current affect with the PANAS-2. Then, the experimenter will affix electrodes and will use Biopac MP150 hardware and AcKnowledge software for data acquisition. All participants will be assessed for baseline negative emotional arousal with psychophysiological (galvanic skin response) measures for five minutes. Then, participants will be randomized to one of three groups:

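### The Aim 1 ANCOVA is valid and meets its stated power, but it leaves unused the same-day affect ratings taken before randomisation, which the trial's own theory suggests are prognostic

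*Combined protocol and SAP*

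**What the plan says.** Under Data Analysis & Statistical Considerations, Specific Aim 1, group differences on the laboratory emotion perception tasks at the training session are tested by ANCOVA, "controlling for their baseline scores assessed in the intake session". No other covariate is named.

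The intake score comes from a separate visit. The Study Overview says that "the participants will return one week later for the training session". Experimental Procedures gives 5 to 7 days as the ideal gap, and Selection of Subjects allows 1 to 14 days, with later returns in some circumstances.

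At the training session, Experimental Procedures lists measures taken from all participants before they are randomised: SUDS, the DSS-4, the Sedation Scale and "7) current affect with the PANAS-2", followed by five minutes of baseline skin response. SUDS, DSS-4, Sedation Scale and PANAS-2 are repeated after the stressor task, immediately before the emotion perception bias task.

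On theory, Background & Significance describes negative emotion as a cause of negative bias, citing work in healthy samples. The Aim 1 text adds: "We also predict that intensity of emotional distress will be related to negative biases in emotion perception". The plan will examine that relationship separately, without naming a model or time point, and Aim 2 treats distress as a mediator.

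**The concern.** The outcome is measured on one day and the only covariate on another. If a person's current emotional state affects how they judge faces, a task score from about a week earlier cannot carry the part of the outcome that reflects how the person arrived on the training day. The trial records that state before allocation and then does not use it in the comparison it is meant to inform.

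Two things are at stake, both modest. The first is precision: variance that a recorded baseline variable could explain stays in the error term. The second is validity conditional on the sample obtained: with 24 analysed per group, arms can differ by chance in arrival affect, and the intake score does not fully correct for this. There is also a gap in specification. Distress is rated both before and after randomisation, and the text does not say which rating, if either, may enter the ANCOVA.

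**Working it through.** **Inputs from the documents.** Alpha 0.05, 72 analysed, 24 per group, f = 0.38, "at least 80% power to detect a medium to large effect size" (Data Analysis & Statistical Considerations). The same section says that "the estimates were derived from a mean difference between conditions" and gives no correlation between covariate and outcome.

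**Assumption.** r is the partial correlation of the pre-randomisation rating with the outcome, given the intake task score. The documents give no value, so a range from 0 to 0.4 is shown.

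**Step 1: the plan's own figure.** For a one-way F test with three groups, the noncentrality is f² × N = 0.38² × 72 = 10.40, with 2 and 69 df and critical F = 3.13. Power is 81.3%, so the stated 80% reproduces; 80% needs f = 0.374. Dropout of 10% to 15% requires 72/0.90 = 80 to 72/0.85 = 84.7, rounded up to 85, so 90 randomised is sufficient.

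**Step 2: the planned ANCOVA.** Take f = 0.38 as already adjusted for the intake score. One covariate leaves 68 error df, and power is 81.32%.

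**Step 3: add one same-day covariate.** Residual variance is multiplied by (1 − r²), so the effect becomes f/√(1 − r²), with 67 error df. The equivalent sample size is 72/(1 − r²).

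| r (assumed) | f/√(1 − r²) | Power | Equivalent N |
|---|---|---|---|
| 0 | 0.380 | 81.3% | 72 |
| 0.1 | 0.382 | 81.7% | 73 |
| 0.2 | 0.388 | 82.9% | 75 |
| 0.3 | 0.398 | 85.0% | 79 |
| 0.4 | 0.415 | 87.8% | 86 |

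At r = 0 the loss is from 81.32% to 81.29%. The gain is under 2 percentage points up to r = 0.2 and just under 4 at r = 0.3.

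**Step 4: chance imbalance.** The standard error of a difference in mean arrival affect between two arms of 24 is √(2/24) = 0.29 SD. A difference above 0.3 SD in either direction in a given pair of arms has probability 2 × [1 − Φ(0.3/0.289)], about 30%. At r = 0.3 it shifts the unadjusted contrast by 0.3 × 0.3 = 0.09 residual SD. The contrast's own standard error is 0.29 residual SD, so the shift is 0.09/0.29, or about 0.31 of one standard error.

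For a rarer imbalance of two standard errors (0.58 SD), the shift is 0.58 × 0.3 = 0.17 residual SD, or 0.6 of a standard error. Given that imbalance, the unadjusted test at a nominal 5% has a conditional type I error of about 8%. Averaged over all randomisations it remains 5%.

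**The case against.** The strongest reply is that nothing in the plan needs correcting. ANCOVA on the baseline value of the outcome is standard and valid, randomisation keeps the contrast unbiased, chance imbalance is already in the standard error, and the stated power is met. All of that stands, and it limits the point to an improvement.

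The second reply is that the prognostic premise is inferred. The theory concerns the emotional state present when faces are judged. Between the arrival ratings and the outcome, every participant hears personal stressors repeatedly, under arm-specific conditions designed to change that state, and the intake score may already carry part of any stable association. This also stands: r may be modest, which is why the range starts at zero.

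Three stronger readings are tempting, and the documents do not support them:

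- A reader might infer that imbalance in arrival distress would push the result towards Hypothesis 1. Chance imbalance is symmetric and can hide the predicted effect as readily as mimic it.
- A reader might infer that the plan ignores distress. It does so only within the ANCOVA: a separate distress analysis is planned for Aim 1 and mediation for Aim 2.
- A reader might infer that the trial is underpowered without the extra covariate. At its own f it is not. Smaller pairwise differences would give lower power, but the documents state none.

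What the replies do not remove is that the data are already collected, the hypothesis gives a reason to use them, and the cost if they prove uninformative is negligible.

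**Conclusion.** The point holds as a missed gain in precision and in validity given the observed arms. It is neither an error nor the correction of a directional bias. At f = 0.38 with 72 analysed, power rises from 81.3% by between nothing (r = 0) and 6.5 percentage points (r = 0.4, 87.8%); a gain of about 2 to 4 points needs r of 0.2 to 0.3. This rests on two assumptions: the unstated r, and reading f = 0.38 as the effect after adjustment for the intake score. The change is worth making because its downside is 0.03 of a percentage point of power, and because it also settles which distress rating may enter the model.

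**What to change.** In the Specific Aim 1 paragraph, pre-specify the PANAS-2 negative affect score from the start of the training session, recorded before randomisation, as a second ANCOVA covariate next to the intake task score.

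In the same place, state that ratings taken after the stressor task are not to be covariates in this model. They follow randomisation, and reduced distress is the proposed pathway, so adjusting for them could remove part of the effect under test. The plan does not propose to do this; the sentence closes an open choice.

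PANAS-2 is preferable to SUDS because the SUDS scale is given as 0–100 under Measures and Tasks, 1–9 at the start of the training session and 0–9 after the stressor. Those passages need to be reconciled before SUDS could serve as a covariate.

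The cost is a sentence or two of text and one error degree of freedom. No extra data collection or change in sample size is needed. The choice should be fixed before outcome data are examined by group.
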